4.9. Pharmacodynamic/Genomics Variables

An optional substudy, which requires separate informed consent, is being conducted to collect DNA from cheek swab samples for future use for the purpose of discovery of predictive biomarkers related to RSV infection and severity.

4.10. RSV Subtyping

RSV subtype analysis will be conducted by RSV-G gene sequencing of RNA derived from the nose swab samples in subjects who tested positive on the RSV Lyra RT-PCR assay. Classification to subtype A and subtype B categories will be performed based on the determined sequence.

4.11. RSV RT-PCR

Study site personnel should evaluate the subject during an unscheduled visit as soon as possible or within 72 hours after receipt of medical attention, including nose swab collections for viral detection. All nose swabs will be tested using the RSV Lyra RT-PCR assay, which will be conducted in a central laboratory.

The central laboratory reports a qualitative result of RSV positive or negative and a quantitative result of cycle threshold (Ct) levels. Ct levels are inversely related to the amount of RSV RNA in the sample.

For infants who do not have an RSV RT-PCR assay for RSV infection done by the central laboratory, study site personnel will obtain and record information about any RSV RT-PCR assays done in a medical facility, including result(s), name of the assay(s) and whether the laboratory(ies) conducting the RT-PCR is a CLIA (Clinical Laboratory Improvement Amendments) certified (or equivalent) laboratory. Type of specimen obtained (nasopharyngeal Swab, nasopharyngeal aspirate, or nasal swab) is collected for local laboratory RSV testing.

4.12. Respiratory Pathogen Panel RT-PCR

An RT-PCR multiplex respiratory panel that includes RSV detection along with detection and identification of other respiratory pathogens will be used as part of the assessment of nasal swab samples. Only RSV negative samples on the RSV Lyra RT-PCR assay will be tested on the multiplex RT-PCR respiratory panel.

The introduction of the use of a multiplex RT-PCR respiratory panel is to explore the alternative etiologies of RSV-negative respiratory tract infections per a comment received from the US FDA while the study was ongoing. RSV test results from the multiplex RT-PCR respiratory panel will **not** be used to derive primary or secondary efficacy endpoints. All efficacy endpoints and RSV detection will be based on RSV Lyra RT-PCR assay as described in the protocol unless otherwise specified in this analysis plan.

5. STATISTICAL METHODS

5.1. Demographics and Baseline Characteristics

Demographic and baseline characteristics (including risk factors as listed in Section 4.1) will be summarized descriptively for all FAS subjects by treatment group (REGN2222 1 dose, REGN2222 2 doses, REGN2222 combined, and placebo), and for the study total. Similar summaries will be made for subjects within each of the 2 stratification factors (ie, gestational age [GA] category and region) as recorded in IVRS/IWRS.

For continuous variables, descriptive statistics will include the following: the number of subjects reflected in the calculation (n), mean, median, standard deviation (SD), minimum, the first and third quartiles (Q1 and Q3), and maximum. For categorical or ordinal data, frequencies and percentages will be displayed for each category.

Other safety baseline data such as vital signs and clinical laboratory measures will be presented collectively in the descriptive statistics summary tables containing respective post-baseline data.

5.2. Medical History

Medical history will be summarized descriptively based on the SAF population by treatment group (REGN2222 1 dose, REGN2222 2 doses, REGN2222 combined, and placebo), and for the study total. Summaries will show subject counts (percentages) by primary SOC and PT. The tables will be sorted by decreasing frequency of SOC in the combined REGN2222 group. Within each primary SOC, PTs will be sorted by decreasing frequency in the combined REGN2222 group.

5.3. Prior/concomitant Illnesses and Medications

Number and percentage of subjects taking concomitant medication will be summarized based on the SAF population by treatment group (REGN2222 1 dose, REGN2222 2 doses, REGN2222 combined, and placebo), and for the study total. The tables will be sorted by decreasing frequency of ATC Level 2, ATC Level 4, and preferred term in the combined REGN2222 group. Number and percentage of subjects taking prior medication will be summarized in a similar fashion to concomitant medication.

5.4. Prohibited Medications

Number and percentage of subjects taking prohibited medication will be summarized by treatment group (REGN2222 1 dose, REGN2222 2 doses, REGN2222 combined, and placebo) and for the study total, for the SAF population. The tables will be sorted by decreasing frequency of ATC level 2, ATC level 4, and preferred term in the combined REGN2222 group.

5.5. Subject Disposition

Subject disposition includes the description of subject status at major milestone decisions in the study.

Subject study status will be summarized by treatment group (REGN2222 1 dose, REGN2222 2 doses, REGN2222 combined, and placebo) and for the study total unless otherwise specified.

Summaries will provide the frequency (and percentage as applicable) of subjects that met the criteria for the following variables:

- Screened subjects (signed the ICF).
- Screen failed subjects.
- Subjects randomized.
- Subjects randomized but not treated.
- Subjects randomized and treated (SAF population).
- Completed study (ie, Day 237 Visit) as collected on the End of Study eCRF page.
- Completed efficacy assessment period (ie, Day 150 Visit) as collected on the End of Study eCRF page.
- Did not complete study (ie, Day 237 Visit).
 - Did not complete efficacy evaluation period (ie, Day 150 Visit) on the End of Study eCRF page.
- Subjects ongoing in the study (only applicable at the time of the first step analysis [see Section 8 for the definition of first step analysis]).
- Primary reasons for discontinuation from study (ie, Day 237 Visit).
- Primary reasons for discontinuation from study for subjects who did not complete efficacy evaluation period (ie, Day 150 visit).

In addition, summary of the number (and percentage) of subjects in each analysis population (as defined in Section 3) will be presented by treatment group, and for the study total. Percentages will be calculated using the number of randomized subjects as the denominator.

The following listing will be provided: A listing of subject disposition including randomization date, dosing date(s), last visit date, completed efficacy evaluation period (ie, Day 150 Visit) or not with reason, completed study (ie, Day 237 Visit) or discontinued by reason; a listing of screening failures and reasons for all screen failed subjects.

5.6. Extent of Study Treatment Exposure and Compliance

5.6.1. Exposure to Investigational product

Exposure to investigational product will be examined based on the SAF population. Descriptive statistics including the number of subjects reflected in the calculation (n), mean, median, SD, minimum, Q1 and Q3, and maximum will be used to summarize the following variables:

- The calculated actual dose (in the unit of mg/kg) of each study treatment.
- Length of observation period.

A tabulation of the number (and percentage) of subjects will be used to summarize the following variables:

- The total number of study doses administered.

- Number of injections received for each dose.
- The number (and percentage) of subjects having observation periods of specific lengths will be summarized according to time period breakdowns as follows: ≥ 1 to < 27 days, ≥ 27 to < 55 days, ≥ 55 to < 80 days, ≥ 80 to < 108 days, ≥ 108 to < 145 days, ≥ 145 to < 168 days, ≥ 168 to < 196 days, ≥ 196 to < 227 days, and ≥ 227 days. These categories are determined by the minimum number of days allowed by the protocol specified windows for scheduled visits.
- The number (and percentage) of subjects having observation periods of at least 27, 55, 80, 108, 145, 168, 196, and 227 days will be presented.

5.6.2. Measurement of Compliance

Study treatment compliance parameters will be examined based on the SAF population. For the compliance ratio (categorical), the frequency (percentage) of subjects will be provided for each category. Descriptive statistics including the number of subjects reflected in the calculation (n), mean, median, SD, minimum, Q1 and Q3, and maximum will be used to summarize the compliance ratio (continuous).

All major and minor protocol deviations potentially impacting efficacy analyses, randomization and drug-dispensing irregularities, as well as other deviations, have been collected and reviewed on an ongoing basis throughout the study as described in the Protocol Deviation Definitions Document (PDDD). Both monitored and CRF derived protocol deviations will be summarized for subjects incurring any major deviation by count and percentage, and subjects incurring each type of major deviation by count and percentage. A subject listing of all major and minor protocol deviations will be provided.

5.7. Analyses of Efficacy Variables

The null hypothesis of the primary efficacy variable is that the proportions of FAS subjects with medically attended RSV hospitalization or outpatient LRTI in the placebo group and in the REGN2222 group are the same ($H_0: p_1 = p_2$). The alternative hypothesis is that the rate for each REGN2222 group is different from the rate for the placebo group ($H_1: p_1 \neq p_2$).

5.7.1. Analysis of Primary Efficacy Variable

The primary efficacy variable is the proportion of subjects with a medically attended RSV infection (hospitalization or outpatient LRTI) during the 150-day efficacy assessment period. Details regarding the derivation of observed primary endpoint event and imputation of missing primary endpoint at Day 150 visit are described in Section 4.6.1.

The primary efficacy variable will be analyzed by CMH statistics with randomization stratum adjusted by the Mantel-Haenzel (MH) method to assess the pairwise comparisons of each REGN2222 treatment arm to placebo. The stratification factors used in the CMH analysis are region and GA per IVRS/IWRS, which will give rise to the following 4 strata:

- North America and ≤ 31 weeks 6 days GA.
- North America and ≥ 32 weeks 0 days and < 35 weeks 6 days GA.
- Rest of the world and ≤ 31 weeks 6 days GA.

- Rest of the world and ≥ 32 weeks, 0 days and < 35 weeks 6 days GA.

This stratum-adjusted difference (ie, absolute risk reduction) based on the MH method is weighted by the harmonic mean of sample size per treatment group for each stratum. Point estimate, 95% confidence interval (CI), and p-value of the proportion difference between 2 treatment groups will be calculated as follows:

If n_{1h} and n_{2h} are the FAS sample sizes of the two treatment groups 1 and 2 in stratum h , then the weight

$$w_h = \frac{n_{1h} n_{2h}}{n_{1h} + n_{2h}}$$

is used for stratum h in calculating the overall difference.

Let $d_h = p_{1h} - p_{2h}$ be the treatment difference in the proportion of subjects with primary endpoint events in stratum h , where p_{1h} and p_{2h} are calculated as:

$$p_{1h} = \frac{e_{1h} + \phi \times n_{1h}}{n_{1h}}, \quad p_{2h} = \frac{e_{2h} + \phi \times n_{2h}}{n_{2h}}$$

with e_{1h} and e_{2h} being the number of subjects with **observed** primary endpoint event(s) in treatment groups 1 and 2, respectively (including ET subjects who had their primary endpoint missing but died prior to Day 150 due to causes adjudicated to be RSV related), n_{1h} and n_{2h} being the number of early termination subjects **missing** the primary endpoint in treatment groups 1 and 2, respectively, and ϕ being the KM estimate of the primary endpoint event rate in all subjects randomized to the placebo group (see Section 4.6.1). Then the point estimate of stratum-adjusted proportion difference is

$$\phi = \frac{\sum w_h d_h}{\sum w_h}$$

The continuity-corrected variance of ϕ is

$$v_{\phi} = \frac{\sum w_h^2 \left(\frac{p_{1h}^* (1 - p_{1h}^*)}{n_{1h} + 1} + \frac{p_{2h}^* (1 - p_{2h}^*)}{n_{2h} + 1} \right)}{2}$$

where

$$p_{1h}^* = \frac{e_{1h} + \phi \times n_{1h} + 0.5}{n_{1h} + 1}, \quad p_{2h}^* = \frac{e_{2h} + \phi \times n_{2h} + 0.5}{n_{2h} + 1}$$

The 95% asymptotic CI of ϕ is $[\phi - z_{0.975} * v_{\phi}, \phi + z_{0.975} * v_{\phi}]$ where $z_{0.975}$ is the 98.75th percentile of the standard normal distribution. The p-value will be computed from the z-score = ϕ / v_{ϕ} . A SAS macro will be used to calculate all the above statistics.

In addition to the absolute risk difference, the stratum-adjusted relative risk of the primary efficacy variable will be provided for the pairwise comparisons of each REGN2222 treatment arm to placebo for descriptive purpose. The number of subjects with primary endpoint event(s)

stratum-specific relative risks will be combined based on the MH method to compute the point estimate and asymptotic 95% CI of stratum-adjusted relative risk using the SAS FREQ procedure. In the event that there are zero table cells in any strata, the exact CI for the relative risk may be computed in lieu of the asymptotic CI by specifying the RELRISK option in the EXACT statement of the SAS FREQ procedure.

The statistical testing of the 2 pairwise comparisons of each REGN2222 treatment arm to placebo for the primary measure will be evaluated at a 2-sided significance level of 0.05 per pairwise comparison, adjusting for multiplicity through a hierarchical inferential approach. In the hierarchy testing sequence, the comparison of REGN2222 2 doses arm to placebo is the first pairwise treatment comparison, and the comparison of REGN2222 1 dose arm to placebo is the second pairwise treatment comparison.

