2.2. Sample Size and Power Considerations

Originally Planned Sample Size

For Part B, the sample size estimation is based on the primary efficacy endpoint of medically attended RSV infection (hospitalization or outpatient LRTI). Literature ([Hall 2009](#), [Ambrose 2014](#)) show that the event rate in this endpoint is in the range of 12% to 22% in the studied infant populations. The Hall data is population based and the majority of infants are full-term; the Ambrose publication of data from the RSV Respiratory Events Among Preterm Infants Outcomes and Risk Tracking (REPORT) study evaluated preterm infants of 32-35 weeks gestational age and less than 6 months of chronological, whom were not receiving RSV prophylaxis. As the event rate may vary over RSV season or geographic region, a relatively conservative approach was taken to assume that event rate is 10% for the placebo group, and either dosing regimen of REGN2222 would reduce the event rate from placebo by 60% (event rate of 4%). With 505 randomized subjects per arm or a total of 1515 randomized subjects, the study would have 90% power to demonstrate a 60% or greater reduction at 2-sided significance level $\alpha=0.025$. This originally planned sample size also incorporated a 5% early dropout rate. The sample size calculation was based on chi-square test with continuity correction and performed using nQuery version 7.0 (Statistical Solutions Ltd, Cork, Ireland).

Based on the originally planned sample size and event rate assumption, we anticipated approximately 90 primary endpoint events.

The blinded sample size re-estimation (as detailed in the study protocol Section 9.2.1) designed for the originally planned sample size has not been performed for this study.

Power Calculation for Reduced Sample Size

[figure not shown]
The sample size of the study has been reduced due to business considerations. The intent of this power calculation is to understand the impact of the reduced sample size on the primary efficacy analysis. Specifically, to accommodate the reduced sample size, the overall Type I error for the pairwise comparisons of each REGN2222 dose regimen to placebo will be controlled using a

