pre-specified hierarchical inferential approach (2-sided $\alpha=0.05$ for each statistical test; see Section 5.7.3), as opposed to the originally planned Bonferroni adjustment (2-sided $\alpha=0.025$ for each pairwise treatment comparison). Therefore, assuming approximately 1200 subjects are administered study drug, the comparison of the REGN2222 2-dose regimen to placebo will have approximately 87% power to detect the previously planned 60% reduction in medically attended RSV infections with a 2-sided significance level of 0.05.

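### SAP 5.7.1 defines the multiplier of the primary 95% confidence interval as the 98.75th normal percentile (2.241) instead of the 97.5th (1.960), so the interval is really 97.5% and can contradict the 0.05-level p-value

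*SAP*

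**What the plan says.** SAP 5.7.1 introduces the primary calculation with "Point estimate, 95% confidence interval (CI), and p-value of the proportion difference between 2 treatment groups will be calculated as follows". After the continuity-corrected variance it gives the interval in a sentence that opens "The 95% asymptotic CI of" and sets the limits at the estimate plus or minus z with subscript 0.975 times v. The same sentence then explains that this z "is the 98.75th percentile of the standard normal distribution".

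The test uses the same ingredients: "The p-value will be computed from the z-score", which is the estimate divided by v. The section closes by saying that each comparison "will be evaluated at a 2-sided significance level of 0.05 per pairwise comparison", with the two-dose arm tested before the one-dose arm. SAP 5.7.3 and protocol 9.5.2.4 set the same 0.05 hierarchy. SAP 2.2 explains that the hierarchy is used "as opposed to the originally planned Bonferroni adjustment", which had put two-sided 0.025 on each comparison.

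**The concern.** The label (95%) and the symbol (subscript 0.975) point to 1.960, while the worded definition points to 2.241. Both cannot be right. The 98.75th percentile is the critical value for two-sided 0.025, the per-comparison level that the plan has abandoned.

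This is the headline effect interval for both dose comparisons. If the worded definition is programmed, the report could declare a comparison significant at 0.05 and move to the next step of the hierarchy, beside a 95% interval that includes no effect.

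The same CMH method is also applied to:

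- the missing-data analyses (SAP 5.7.1.3);
- the components of the composite (5.7.1.4);
- the site and stratification sensitivity analyses (5.7.1.5, 5.7.1.6);
- the subgroup intervals and forest plots (5.7.1.7);
- the secondary endpoint (5.7.2);
- several exploratory proportions (5.7.4).

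**Working it through.** **1. Which alpha the current design uses.** Inputs from SAP 2.2: 10% on placebo, 4% on REGN2222, continuity-corrected chi-square test, 5% dropout.

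- *Original plan, two-sided 0.025, 90% power.* The uncorrected size is [2.2414 × √(2 × 0.07 × 0.93) + 1.2816 × √(0.10 × 0.90 + 0.04 × 0.96)]² / 0.06² = 447 per arm. The continuity correction raises this to 480, and 480/0.95 = 505.3, against the stated 505. The figure reproduces.
- *Reduced plan, about 1200 subjects, two-sided 0.05.* 400 per arm less 5% is 380. Removing the continuity correction, 380 × (1 − 1/(380 × 0.06))² = 347.4. Power = Φ[(√347.4 × 0.06 − 1.960 × 0.3608)/0.3583] = 87.4%, against the stated 87%. At two-sided 0.025 it would be 80.6%.

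The current power statement therefore rests on 0.05, for which the critical value is 1.960.

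**2. Level of the interval.** A symmetric normal interval with multiplier z(q) has level 2q − 1.

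| Percentile | z | Level of interval | Excludes zero when |
|---|---|---|---|
| 97.5th | 1.960 | 2 × 0.975 − 1 = 95.0% | p < 0.05 |
| 98.75th | 2.241 | 2 × 0.9875 − 1 = 97.5% | p < 0.025 |

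The width ratio is 2.2414/1.9600 = 1.144. A one-sided reading does not rescue the wording, because the 98.75th percentile would give a 98.75% one-sided bound. Interval and test disagree when 1.960 < |z| < 2.241, that is, when 0.025 < p < 0.05.

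**3. Worked example.** The counts are assumed: one stratum, 400 per arm, no missing data, 24 events on active and 40 on placebo. The SAP's smoothed proportions are (24 + 0.5)/401 = 0.0611 and (40 + 0.5)/401 = 0.1010.

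- Standard error = √(0.0611 × 0.9389/401 + 0.1010 × 0.8990/401) = 0.01922
- Difference = 0.06 − 0.10 = −4.00 points; z = −0.0400/0.01922 = −2.081; p = 0.037
- With 1.960: −7.77 to −0.23 points
- With 2.241: −8.31 to +0.31 points

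With 23 against 40 events, p = 0.026 and the two intervals are −7.99 to −0.51 and −8.53 to +0.03.

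**4. How often the conflict would arise.** With 400 per arm, 10% on placebo and no dropout, let m be the true difference divided by its standard error. The chance is approximately Φ(2.241 − m) − Φ(1.960 − m).

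| Active rate (5% and 6% assumed) | m | Chance of conflict |
|---|---|---|
| 4% (as planned) | 0.06/0.01792 = 3.349 | 5.2% |
| 5% | 0.05/0.01854 = 2.697 | 9.4% |
| 6% | 0.04/0.01913 = 2.091 | 11.2% |

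A simulation of the stratified SAP statistic used 12,000 trials with rates of 10% and 4%, 400 per arm, four strata, 5% uniform dropout and Kaplan-Meier imputation. It gave p < 0.05 in 89.7% of trials, while the 2.241 interval excluded zero in 83.2%. The gap is 6.5 points, about 1 trial in 15.

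**The case against.** The best counter-argument is that the SAP contradicts itself rather than firmly specifying 2.241. The 95% label, the subscript and the 0.05 test level all point to 1.960, and only the worded gloss disagrees. A programmer who followed the label would get the right interval, and the macro is not in the documents, so no coding error has been seen. This stands as a limit on what can be claimed. It does not remove the problem: the gloss is the only place where the percentile is spelled out, and someone programming independently from it would produce a different headline interval.

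It is also true that no confirmatory decision changes. The p-value does not use the multiplier, the hierarchy runs on p-values, and an interval built with 2.241 is too wide, so it cannot overstate benefit. Nor does every interval use this constant: the relative-risk, odds-ratio and hazard-ratio intervals come from SAS FREQ, SAS LOGISTIC and Cox regression, and the subgroup intervals are descriptive.

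Finally, the 24 against 40 example was chosen to fall in the conflict zone and is a 40% reduction, not the planned 60%. The stratum sizes and dropout timing in the simulation are assumed. That the percentile is left over from the Bonferroni plan is an inference: no document says so, and SAP 1.2.4 describes this as the first version.

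**Conclusion.** The concern holds. As worded, the multiplier is wrong for a 95% interval: it gives 97.5%, 14.4% wider than intended, and does not correspond to the two-sided 0.05 test reported beside it. The consequence is a possible contradiction between interval and p-value when p lies between 0.025 and 0.05. Under the planned effect its probability is roughly 1 in 15 to 1 in 20, depending on the dropout assumption; with active rates of 5% or 6% it rises to about 9% to 11% without dropout. Type I error, power, point estimates and the order of testing are untouched.

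The percentile, level and width results are exact. The worked example and the conflict probabilities rest on the assumed counts, rates and dropout above, and treat the printed v as a standard error, because the text available for this check does not show a square root.

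**What to change.** In SAP 5.7.1, change 98.75th percentile to 97.5th percentile and state the value, 1.960. Before database lock, confirm that the SAS macro uses 1.960, for the primary comparisons and for every analysis that reuses this CMH method, and correct it if it does not. The interval will then exclude zero exactly when the two-sided p-value is below 0.05. The cost is one number in the SAP and a check of one constant in the code, with no effect on data collection, design or sample size.
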